### ***Second Follow-up Photo (27-31 days after Visit 1)***

Subject will be asked to send a photo of his treated fingers to MGH security email. The photos must be taken from the fingers and areas where the device has been applied. The photos will be sent by encrypted MGH email.

An optional visit can be requested by the investigator if he cannot evaluate the treated area by the photos or if he believes in person visit is needed for better clinical assessment.

#### **Drugs to be used**

No therapeutic drugs will be used in this study.

#### **Devices to be used**

#### **Experimental Cooling Device description**

The experimental device is a cooling device intended to provide analgesia during needle sticks for blood draws on digits extremities. The device is a circulating fluid chiller using a propylene glycol / water mixture (4:7) flowing through an applicator designed to cool the conductive nerves in the digit to a temperature below which nerve conduction from the distal portion of the digit reduces and/or ceases. The device is designed with two u-shaped coolant tubes that are applied to the circumference of tissue at the base of a digit. The coolant tubes appose each other to surround the digit and then are brought together with a screw /spring mechanism to apply sufficient pressure to the main arteries feeding the digit to partially occlude blood flow, thereby enhancing the tissue-cooling effect.

The clinician monitors tissue blanching while applying the applicator to ensure there is sufficient but not excessive occlusion.

With a circulating coolant temperature of -3°C, the device will cool tissue in contact with and near proximity to the cooling tubes to 0°C to 7.5°C. The subject's hand will be wearing an sterile glove to provide a barrier between the cooling ring and skin. The fifth finger of the glove will be removed sufficiently to expose the area to be pricked in this study. This circumferential ring of cold and partially occlusive pressure on the digit will provide analgesia by blocking nerve conduction signals from leaving the digit and signaling pain to the central nervous system. The pressure on the arterial vessels assists tissue cooling by reducing blood flow and therefore the amount of heat transferred to the cooled tissue.

This device poses no risk to the subject if left on for 10 minutes or less. The device will only be on the subject for 7 minutes, and glycerol will also be used to further decrease any risk to the subject.

#### Thermal camera

##### Flir A655SC Thermal Camera A600 Series

A thermal camera will be used to take a video recording of the subjects' "chilled" and "control" hands during the first study visit to detect temperature differences of the treatment area. Video recording will start before the device's application and will continue until the post-procedure pictures have been taken. The device will be removed, and thermal images of the treatment area will be obtained.

#### Video Recording

An encrypted iPhone 12 Pro camera will be used by study staff (investigator or research coordinators) to take a video recording from the subjects' chilled hand during the first study visit. Video recording will start before the device's application and will continue until the post-procedure pictures have been taken.

Videos will be blindly reviewed by a physician and assessed using temperature grading scale. All video recording data files will be labeled with the study subject number. No identifying information will be used in labeling the video data files and the files will be stored on Partners Dropbox. The videos will be stored at Partners Dropbox until 7 years after the end of this study when all the copies will be permanently deleted from this drive. Only study staff will have access to the videos (for storage purposes- like research coordinators or for assessment - investigators).

#### **b. Data to be collected and when data is collected**

Study data will be collected during screening and study visit. Study data to be collected includes Subject's reported pain scores with Wong-Baker pain rating scale, subjects' oximeter readings, subjects' video recording, subjects' photographs, and photographs of the Whatman 903 filter papers containing subjects' blood drops.

**c. Remuneration**

Subjects will receive \$150 for completing Visit 1. The total remuneration amount will be \$ 150 for completion of all study visit.

We will also provide a parking voucher for each visit upon request.

**7. Risks and Discomforts**

**a. Complications of prick procedure**

The complications of prick include pain, swelling, edema, redness, and bruising.

**b. Device complications/malfunctions**

The device is designed to apply pressure to the two main feeder vessels to the digit. The pressure applied is controlled by the study physician who will monitor tissue blanching based on their clinical experience to ensure an appropriate amount of pressure/occlusion. In addition to monitoring pressure through tissue blanching, this study will limit the amount of time the device can be applied to the digit to 5 minutes. This time limit will be sufficient to prevent tissue ischemia, especially with the tissue cooling that will also be applied.

The device is designed to circulate propylene glycol cooling fluid at -2.5 degrees C. There are temperature indicators on the inlet and outlet tubing to the finger chiller. Temperature indicators will be checked and confirmed to be at the correct operating temperature prior to applying the device to subjects and during the finger pricking procedure.

If there were a leak of cold propylene glycol onto a subject's or study staff's skin, the temperature of the cooling fluid is not cold enough to cause significant damage. The propylene glycol portion of the cooling fluid in the system is a food-grade propylene glycol conforming to United States Pharmacopeia standards and is GRAS. According to the safety data sheet, it is considered to have low toxicity and may cause mild skin irritation. If the system is found to be leaking cooling fluid during the study, study staff will immediately remove the device from the subject and wipe the leaked fluid from the subject's or staff's skin. Study staff will clean the affected area in accordance with standard cleaning procedures for intact skin.

The circulating fluid is chilled and pumped by a commercially available liquid chiller. If the chiller fails to maintain the circulating fluid temperature or if the pump stops pumping fluid, the temperature of the finger cooling device may rise, the device may not provide sufficient analgesia to the tissue and the subject may feel pain. If the chiller fails to maintain the -2.5 temperature or the pump fails to circulate the fluid, the inlet and outlet temperature sensors near the clamp will rise, providing feedback to the

clinician to stop the experiment. Subjects will be instructed by study staff to immediately report any pain to the study physician performing the treatment. The subject has the right to stop the study at any time if they feel pain or otherwise wish to stop the study.

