  - No more than one minute after sterile glove application, the novel digit cooling device will be applied to the “chiller” digit on the area with glycerol.
  - No more than four minutes after the novel digit cooling device is applied to the “chiller” finger, one prick will be applied to the ventral tip of the “chiller” digit. A pain score will be reported by the subject.
  - The pricked finger will subsequently be held over a single-use Whatman 903 filter paper. Approximately every ten seconds after the prick, the filter paper will be gently applied to the blood drop to absorb the blood. This will be repeated on new locations of the filter paper until blood flow stops. At least one Whatman 903 filter paper will be used per finger prick. The Whatman 903 filter paper will be imaged.
- Post-procedure images will be taken of the tips of the “control” and “chiller” digits.
- A thermal camera will be used to video record the fingers starting with the sterile glove application on the “chiller” finger until the post-procedure images have been collected by an encrypted iPhone 12 Pro.
- Regular video recording with an encrypted iPhone 12 Pro will be done simultaneously.

Wong-baker pain assessment on a visual analog pain scale:

©1983 Wong-Baker FACES Foundation. [www.WongBakerFACES.org](http://www.WongBakerFACES.org)  
Used with permission. Originally published in *Whaley & Wong's Nursing Care of Infants and Children*. ©Elsevier Inc.

- The device will be removed from the digit
- Study staff will document any anticipated side effects or Adverse Events that occur during the study visit.
- A licensed physician investigator will be operating the study device during the procedure.

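### Section 7.b caps device time at 5 minutes while the device description plans 7, and the coolant temperature is given as both -2.5 °C and -3 °C

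*Combined protocol and SAP*

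**What the plan says.** **Device time.** Section 7.b (Device complications/malfunctions) says "this study will limit the amount of time the device can be applied to the digit to 5 minutes", and then: "This time limit will be sufficient to prevent tissue ischemia". The Experimental Cooling Device description in section 6 says "The device will only be on the subject for 7 minutes". The sentence before that one reads "This device poses no risk to the subject if left on for 10 minutes or less".

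The Visit 1 steps in section 6.a give no total device time. The prick on the chilled finger comes "No more than four minutes after the novel digit cooling device is applied". Blood is then blotted about every ten seconds, and "This will be repeated on new locations of the filter paper until blood flow stops". The line "The device will be removed from the digit" appears later in the list, after blood collection and the post-procedure images, with no clock time. The Thermal camera section runs the video until the post-procedure pictures are taken and then says "The device will be removed, and thermal images of the treatment area will be obtained".

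**Coolant temperature.** Visit 1 has the device brought to -3 °C before the procedure, and the device description also gives -3 °C as the temperature of the circulating coolant. Section 7.b gives -2.5 °C twice: as the temperature at which the fluid is designed to circulate, and as the temperature whose loss marks a chiller failure. The same section has staff confirm the correct operating temperature before application and during the pricking.

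**The concern.** The 5-minute figure is a safeguard. It is the limit on which section 7.b bases its statement about ischemia, alongside the physician's visual judgement of blanching. If the procedure is planned at 7 minutes, the planned session lies outside the condition for which that reassurance is given. The subjects are healthy volunteers (section 3) with no medical benefit to expect (section 8.a), so the stated risk limit and the stated procedure ought to agree.

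There is also a practical consequence. Staff who remove the device at 6 minutes cannot tell from the protocol whether they have complied or deviated. The monitor, who under section 10.a confirms that procedures were done correctly, has no single standard to apply.

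The temperature conflict is smaller but of the same kind. The operating-temperature check has two possible reference values and no tolerance. A reading that has risen from -3 °C to -2.5 °C departs from Visit 1 and the device description, yet is on target under section 7.b.

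**Working it through.** The plan has no derived figure to reproduce. The check sets the statements side by side and takes differences.

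| Item | Section | Value |
|---|---|---|
| Limit on device application | 7.b | 5 min |
| Time the device is on the subject | 6, device description | 7 min |
| Duration described as posing no risk | 6, device description | 10 min or less |
| Application to prick | 6.a, Visit 1 | up to 4 min |
| Maximum total device time | 6.a, Visit 1 | not stated |
| Coolant, before the procedure | 6.a, Visit 1 | -3 °C |
| Coolant, circulating | 6, device description | -3 °C |
| Coolant, design value and failure condition | 7.b | -2.5 °C (twice) |

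**Step 1: the two device times.** 7 - 5 = 2 minutes, and 7/5 = 1.40, so the planned time is 40% longer than the limit. Both figures describe how long the same device is on the digit, and both are below 10 minutes.

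**Step 2: do the Visit 1 steps settle it?** They do not. If the prick comes at the latest permitted moment, 4 minutes, the device time left afterwards is:

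- under the 5-minute limit: 5 - 4 = 1 minute
- under the 7-minute figure: 7 - 4 = 3 minutes
- under the 10-minute statement: 10 - 4 = 6 minutes

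If the device stays on during blood collection, bleeding longer than 1, 3 or 6 minutes respectively passes each figure. The documents give no bleeding time. As an illustration, assume bleeding of 0.5 to 5 minutes and, as a second assumption, an earlier prick at 2 minutes. Device time is prick time plus bleeding time, before any imaging:

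| Assumed bleeding (min) | Prick at 4 min | Prick at 2 min |
|---|---|---|
| 0.5 | 4.5 | 2.5 |
| 1 | 5 | 3 |
| 2 | 6 | 4 |
| 3 | 7 | 5 |
| 5 | 9 | 7 |

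Overrun of the 5-minute limit is therefore possible but not certain. It depends on removal following collection, which the text suggests but does not fix.

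**Step 3: the two temperatures.** -2.5 - (-3) = 0.5 °C. The gap cannot be read as a pre-chill setting against a circulating temperature, because the device description gives -3 °C as the circulating temperature and section 7.b gives -2.5 °C for the same circulating fluid.

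**Step 4: effect on the analysis.** The pain score is reported at the prick, at most 4 minutes after application and so inside both device times. The time conflict does not alter it. Neither conflict enters the sample-size statement in section 9.

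**The case against.** The best case for leaving the text alone is that both durations fall within the 10 minutes described as free of risk, that a physician operates the device and watches for blanching, that subjects are told to report pain and may stop, and that follow-up photographs are collected. All of this is in the protocol. None of it sets a duration, however, and section 7.b does not appeal to the 10-minute statement, so the conflict between a 5-minute limit and a 7-minute plan remains.

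Three narrower objections carry some weight:

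- **Late removal is not shown.** The Visit 1 bullets are not in strict time order: video recording is listed after the pricks although it starts at glove application. The Thermal camera section puts removal after the pictures but does not mention blood collection. The bleeding scenarios therefore rest on assumed inputs, and the finding does not depend on them.
- **The temperature gap is minor by itself.** Section 7.b describes failure as warming, with weaker analgesia as the consequence, and the documents attach no injury to a 0.5 °C difference. It matters only because the required check has two reference values.
- **The Visit 1 and Thermal camera sections contain no conflicting total time.** Adding a removal point there is a clarification that follows from settling the time elsewhere.

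**Conclusion.** The concern holds, and the text must be corrected. As written, a session that follows the device description breaches a safety limit on which the risk section relies, by 2 minutes or 40%. This rests on no assumption; it is a direct comparison of two current statements, with no reconciling text anywhere in the protocol. The coolant temperatures differ by 0.5 °C, a secondary inconsistency that leaves the operating-temperature check without a single reference. Whether an actual session would exceed 5, 7 or 10 minutes under the Visit 1 steps depends on prick time, bleeding time and the removal point, which the documents leave open. The point concerns the safety text. It gives no reason to doubt the timing of the primary pain score or to revisit the sample size, and it takes no position on which time or temperature is right.

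**What to change.** The sponsor and investigator should:

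1. Reconcile section 7.b and the device description to one device time of their choosing, and state how the 10-minute statement relates to it.
2. Carry that time into the Visit 1 steps with an explicit removal point consistent with it, and align the order given in the Thermal camera section.
3. Reconcile Visit 1, the device description and section 7.b to one coolant temperature of their choosing.
4. Name the reading against which the temperature check and the chiller-failure condition in section 7.b are judged.

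The cost is protocol wording in those four places (Visit 1, the device description, Thermal camera and section 7.b), including one explicit removal line. No additional subjects, visits or equipment are needed.

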#### *Visit 1*

Visit 1 is expected to last approximately 1 hour.

The following assessments will be performed during Visit 1:

- Review of eligibility criteria
  - Ring size measurement
- Review of medical history and medications
  - Urine pregnancy test (for female participants of childbearing potential)
- Take blood pressure (2 times before treatment; 2 times after) using a standard hospital owned blood pressure arm cuff device.
- The novel digit cooling device will be turned on and allowed to chill to -3 degrees Celsius prior to the procedure.
- Two fingers (one on each hand) will be pricked during Visit 1: the “control” digit and the “chiller” digit.
  - The first finger to be pricked will be randomized.
  - The pricked fingers will be either the fifth or third digit(s).

- Pricks will be administered using a sterile and disposable McKesson Push-Button 17G or 23G Safety Lancet, bought specifically for this trial.
- Subjects will be instructed on how to report a pain score for each prick. A visual 10-point pain scale will be used (see below).
- The procedure for the “control” digit is as follows:
  - A Beurer oximeter will be used to measure the percent oxygen and pulse rate.
  - A thermal camera will be used to measure the temperature of the finger tip.
  - One prick will be applied to the ventral tip of the “control” digit. A pain score will be reported by the subject.
  - The pricked finger will subsequently be held over a single-use Whatman 903 filter paper. Approximately every ten seconds after the prick, the filter paper will be gently applied to the blood drop to absorb the blood. This will be repeated on new locations of the filter paper until blood flow stops. At least one Whatman 903 filter paper will be used per finger prick. The Whatman 903 filter paper will be imaged.
- The procedure for the “chiller” digit is as follows:
  - A sterile glove will be placed on the “chiller” hand. The top of the fifth or third finger of the glove will be cut and rolled down to the base of the finger to promote venostasis and blood harvesting.
  - A Beurer oximeter will be used to ensure there is not enough blood flow to measure the percent oxygen and pulse rate in the finger.
  - A thermal camera will be used to measure the temperature of the finger tip.
  - A layer of glycerol will be applied circumferentially to the intended treatment area on the “chiller” digit.

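### The risk section caps cooling-device time at 5 minutes to prevent ischaemia, but the device description plans 7 minutes; the rolled glove has no written end time

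*Combined protocol and SAP*

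**What the plan says.** Two places in the combined protocol and SAP give the time that the device spends on the finger.

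- Section 7.b, Device complications/malfunctions: "this study will limit the amount of time the device can be applied to the digit to 5 minutes". The next sentence gives the reason: "This time limit will be sufficient to prevent tissue ischemia".
- Section 6, Experimental Cooling Device description: "The device will only be on the subject for 7 minutes". The sentence before it says that the device carries no risk if left on for up to 10 minutes.

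The Visit 1 steps (Section 6.a) state neither figure. For the chiller digit they run as follows:

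- The tip of the glove finger "will be cut and rolled down to the base of the finger to promote venostasis and blood harvesting".
- With the glove rolled, and before the device goes on, flow is checked: "A Beurer oximeter will be used to ensure there is not enough blood flow to measure the percent oxygen and pulse rate in the finger".
- The device comes next: "No more than one minute after sterile glove application, the novel digit cooling device will be applied".
- The prick follows: "No more than four minutes after the novel digit cooling device is applied".
- Blood is blotted about every ten seconds, with no time cap: "This will be repeated on new locations of the filter paper until blood flow stops".
- A later bullet removes the device. It does not mention the glove.

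The Thermal camera section also has the device removed, and then thermal images taken of the treated area. It does not mention the glove either.

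**The concern.** The 5-minute limit is the written basis for telling healthy volunteers, who have no health benefit from taking part (Section 8.a), that the pressure on the digital arteries will not cause ischaemia. A safety limit should have one value wherever it appears. Here an operator who relies on the device description would plan a duration that the risk section does not allow.

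The lesser point concerns what the limit covers. By the plan's own oximeter check, flow in the finger is already too low to read once the glove is rolled, before the device clock starts. The removal step then names only the device, so the rolled glove has a written start but no written end.

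**Working it through.** No sample-size or power figure is involved. The check sets the texts side by side and adds times.

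**Inputs**

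| Quantity | Value | Source |
|---|---|---|
| Device limit | 5 min | Section 7.b |
| Planned device time | 7 min | Section 6, device description |
| Device time called free of risk | 10 min | Section 6, device description |
| Glove application to device | at most 1 min | Section 6.a, Visit 1 |
| Device application to prick | at most 4 min | Section 6.a, Visit 1 |
| Blotting interval | about 10 s | Section 6.a, Visit 1 |

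**1. Conflict between the two device times.** 7 − 5 = 2 min. Could the 5 minutes be 1 minute of glove plus 4 minutes to the prick? The sum is right, but Section 7.b defines the figure as time with the device applied, so that reading does not fit.

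**2. Glove plus device, if both come off together.** Total = glove lead time + device time.

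- Section 7.b: 1 + 5 = 6 min at most.
- Device description: 1 + 7 = 8 min at most.

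The 1 minute runs from glove application, so the time from roll-down is somewhat shorter. If the glove stayed on after the device, that time would be added, and the plan sets no limit on it.

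**3. Time left for blood collection with the device on.** Assume the prick comes at the 4-minute maximum and the device stays on during blotting. The documents do not state the second assumption, but the removal bullet comes after the blotting bullets.

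- 5-minute limit: 5 − 4 = 1 min, or 60/10 = about 6 blots.
- 7-minute statement: 7 − 4 = 3 min, or 180/10 = about 18 blots.
- Difference: 2 min, about 12 blots.

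So the choice of figure matters in practice. Blotting runs until bleeding stops, and staff need to know when the device must come off if that takes longer than a minute.

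**4. Comparison with the 10-minute figure.** 6 < 10 and 8 < 10. The 10-minute statement is about the device; it does not mention the rolled glove as a constriction.

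**The case against.** The strongest case for the plan is that this is one inconsistent sentence with little clinical weight. Only Section 7.b states a limit and ties it to ischaemia. The 7 minutes is a planned duration in a device description, next to a statement that 10 minutes is free of risk. This is right, and a reader who inferred that the safeguard itself contains two rival limits would go too far. It does not remove the conflict, because a planned 7 minutes cannot satisfy a limit of 5.

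On the glove, a licensed physician operates the device and would very likely take the glove off as well. Imaging the treated area after device removal may require the glove to be moved. This stands too: what is missing is a written step and time, and nothing suggests that the glove would be left on. Nor does an oximeter that cannot read prove zero flow, so a glove minute need not equal a device minute.

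The plan has other safeguards: exclusion of cold-induced disease and vasculitis (Section 4.a), blanching checks, pain reporting and the right to stop (Section 7.b), adverse-event recording, post-procedure images and two follow-up photographs. They lower the expected harm, but none settles which device time applies or when the glove comes off. Pain reporting is also a weak alarm here, because the device is meant to block pain signals from the digit.

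A reader might also infer that 6 or 8 minutes is dangerous, or that 6 minutes should become a formal cap on total constriction. The documents support neither. They show no injury at those times, and 6 is only 1 + 5, with no support as a threshold.

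**Conclusion.** The point holds as a minor inconsistency in a safety figure. The device description exceeds the Section 7.b limit by 2 minutes (7 against 5), and no text reconciles the two. The lesser point is that glove plus device can reach 6 or 8 minutes and the glove has no written end. These totals are upper bounds; they assume the full 1-minute lead and release of both together. The glove minute breaches no stated limit, because none covers it.

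Exposure is one chiller finger in each of 12 planned subjects, and expected harm is low. Taking 5 minutes as the governing figure assumes that the sponsor means the number tied to ischaemia prevention.

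**What to change.** 1. **Device description (Section 6).** Replace the 7-minute statement with: *The device will be on the subject for no more than 5 minutes.*
2. **Visit 1 removal bullet (Section 6.a).** Change it to: *The device and the rolled glove will be removed from the digit no later than 5 minutes after device application.* Record the removal time beside the blots.
3. **Optional.** Record a repeat reading after removal with the oximeter already at the visit. Do not attach an automatic adverse-event rule, since no waiting time or pass criterion has been set and a cold finger may give no reading.

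**Cost.** Two wording changes and one recorded clock time, plus the repeat reading if it is used. The real cost falls on Aim 2, the quantity of blood collected. With a prick at the 4-minute maximum, any blotting beyond 1 minute would be done after release of both device and glove. The glove is rolled partly to help blood collection, so release may slightly change the chiller-digit quantity, and the documents do not show in which direction. Measured against the 7-minute statement, up to 2 minutes (about 12 blots) of collection with the device on would be lost. Measured against Section 7.b, device time does not change and only the glove release is new. The recorded removal time shows which blots came after release; it does not undo the change in conditions. Pricking earlier than the 4-minute maximum would leave more time before release.
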